5.4 Removal of Patients from the Genotype-guided Tacrolimus Therapy

Removal of patients from the genotype-guided tacrolimus therapy can occur for the following reasons:

- 1) Extraordinary medical circumstances: If, at any time the constraints of this protocol are detrimental to the patient's health, then the patient may be removed from the genotype-guided tacrolimus therapy. In this event, the investigator will do the following:
 - Notify the UNC-CH Principal Investigator
 - Document the reason(s) for withdrawal on flow sheets or Case Report Form (CRF)

- Notify the IRB

- 2) Voluntary withdrawal
- 3) Excessive toxicity: Patients who experience any grade III or grade IV AE deemed by the Principal Investigator to be related to tacrolimus therapy
- 4) Investigator's judgment: When deemed in the best interest of the patient by their attending physician, patients should be removed from the study and included in the intent-to-treat (ITT) analysis.
- 5) Premature closure of the study: This study may be prematurely terminated, if in the opinion of the investigator there is sufficient reasonable cause. Written notification documenting the reason for study termination will be provided by the investigator.
- 6) Circumstances that may warrant termination include, but are not limited to:
 - Determination of unexpected, significant, or unacceptable risk to patients
 - Failure to enter patients at an acceptable rate
 - Insufficient adherence to protocol requirements
 - Insufficient complete and/or evaluable data

6 Study Drug

6.1 Description

Please refer to the current FDA-approved package insert (Attachment 4) for tacrolimus for clinical background information and possible side effects.

6.2 Treatment Regimen

All patients who consented will undergo genotype testing prior to transplant. The genotype-guided dosing recommendation as shown in **Figure 3** below only refers to the initial tacrolimus dose. Subsequent tacrolimus dosing will then be adjusted according to trough concentrations and desired therapeutic concentrations. Therapy for oral tacrolimus will be prescribed by the kidney transplant team as part of a standard immunosuppression agent given to kidney transplant recipients starting at 0.1 mg/kg/day (nonexpressers) or 0.2 mg/kg/day (expressers) given in 2 divided doses; maximum total daily dose of tacrolimus is 20 mg/day.

As the drug and the doses being used are not investigational, tacrolimus will be stored and dispensed in accordance to current UNC-CH pharmacy procedures. The patients and investigators will not be blinded in the study, hence there will be no procedure related to blinding of study drug.

6.2.1 Pharmacogenomic-guided dosing algorithm for the initial tacrolimus dose

The pharmacogenomic-guided algorithm is described in **Figure 3** below. The genotype-guided dosing recommendation only refers to the initial tacrolimus dose. Subsequent tacrolimus dosing will then be adjusted according to trough concentrations and desired therapeutic concentrations.

Figure 3: Pharmacogenomic-guided Dosing Schematic

[figure not shown]

Figure 3 illustrates the genotype-guided dosing for the CYP3A5 expressers and nonexpressers for the initial tacrolimus dose following kidney transplantation.

6.2.2 Therapeutic Target Concentrations

The drug will be adjusted and monitored using current UNC-CH standard kidney transplantation treatment procedure to reach the following therapeutic target levels:

- 8-10 ng/mL during 0 to 4 months of treatment
- 6-8 ng/mL during 5 to 12 months of treatment
- 5-7 ng/mL at >12 months of treatment

Therapeutic drug monitoring, which provides a measure of compliance, will also be conducted according to standard UNC-CH procedure.

7 Study Procedures

Efficacy and safety measures will be assessed throughout the study. All study procedures will be conducted in accordance to applicable regulatory and ethical requirements.

The schedule of events prior to pharmacogenomic intervention and during the Intervention and Follow-up periods are briefly described below and is summarized in **Table 1**.

7.1 Pre-intervention Assessments

The following procedures will be performed at Study Day 0, prior to initiation of the genotype-guided initial tacrolimus dose

- Screening for eligibility
- Acquisition of informed consent
- Buccal swab sample collection
- Hematology, clinical chemistry, urinalysis, eGFR, medical history, and physical exam

- Genotyping

7.2 *Pharmacogenomic Intervention*

On Study Day 1, Eligible patients who consented will receive genotype-guided dosing only for the initial tacrolimus dosing (0.1 mg/kg/day for CYP3A5*3/*3 or 0.2 mg/kg/day for CYP3A5*1/*1 or CYP3A5*1/*3). In addition, the following safety and efficacy parameters will be collected: hematology, clinical chemistry, urinalysis, adverse event (AE) and renal function assessments, medical history, physical exam, tacrolimus levels, and immunosuppressive and tacrolimus therapy modifications.

7.3 *Post-intervention or Follow-up Assessments*

Following administration of the initial genotype-guided tacrolimus dose, protocol-driven therapy will cease, and standard of care for tacrolimus dose adjustment and monitoring will be initiated. Efficacy and safety data, including AE assessments, renal function, and tacrolimus levels, will still be collected at each subsequent standard follow-up interval post Study Day 1 and up to 12 months of the initial tacrolimus dose.

Table 1: Schedule of Events

Procedure	Study Day 0	Study Day 1	3-day Follow-up	7-day Follow-up	Week 2 Follow-up	Week 3 Follow-up	Week 4 Follow-up	3-month Follow-up	6-month Follow-up	9-month Follow-up	12-month Follow-up
Screening	x										
Informed consent	x										
Buccal swab sample	x										
Medical history	x										
Drug therapy assessment	x	x	x	x	x	x	x	x	x	x	x
Physical Exam	x	x	x	x	x	x	x	x	x	x	x
Clinical chemistry	x	x	x	x	x	x	x	x	x	x	x
CBCs with differentials	x	x	x	x	x	x	x	x	x	x	x
Urinalysis	x	x	x	x	x	x	x	x	x	x	x
CrCl	x	x	x	x	x	x	x	x	x	x	x
eGFR	x	x	x	x	x	x	x	x	x	x	x
Genotyping	x										
Initiation of genotype-guided dose		x									
Tacrolimus level		x	x	x	x	x	x	x	x	x	x
AE assessments ¹		x	x	x	x	x	x	x	x	x	x
Efficacy assessments ²		x	x	x	x	x	x	x	x	x	x

Abbreviations: AE=adverse event; BPAR = biopsy proven acute rejection; CBC = complete blood count; CrCl = creatinine clearance; eGFR = estimated Glomerular Filtration Rate.

¹The AE assessment will be conducted using the AE form (see AE Attachment). AEs may be assessed during an in-person clinic visit or a scheduled phone call.

²Episodes of rejections will be assessed as part of the efficacy assessments. Information from biopsies, if collected, will also be assessed.

8 Statistical Plan

8.1 General Considerations

This is a prospective, single-center study aimed to assess the efficacy and tolerability of the initial genotype-guided tacrolimus dosing following kidney transplantation. Proper use of the study design will be ensured by the study investigators informing the study statistician, [name]. Additionally, quarterly follow-up on patient accrual will be initiated by the study investigators as further assurance of compliance with the design of the study laid out in this protocol.

The term “pharmacogenomic group” will refer to prospective patients who received genotype-guided dose for the initial tacrolimus dose. The term “control group” will refer to age- and disease-matched eligible patients who received the standard tacrolimus dose after kidney transplantation from 2010 to the end of study period.

8.2 Sample Size Determination

The primary endpoint of this study is to evaluate the proportion of patients reaching target levels (8-10 ng/ml) on day 3 and day 7 after kidney transplantation.

We calculated that a total study population of 260 patients (pharmacogenomics group = 130; control group = 130 patients) would be sufficient to provide a statistical power of 90% to detect a significant difference between the two groups, on the basis of a two-sided χ^2 test, a significance level of 5%, a frequency of approximately 50% for the *CYP3A5*3/*3* genotype, and a 40% and 60% frequency of the primary endpoint in the control and pharmacogenomic group (Thervet et al. 2010), respectively. Because of the nature of the study design we anticipate a small rate of sample dropout (<5%), which should not appreciably impact the power of the study.

8.3 Statistical Methods

All analyses will be performed on the basis of the ITT principle. Unless stated otherwise, the term “descriptive statistics” will refer to the number of subjects, mean, median, standard deviation, minimum, and maximum for continuous data and to frequencies and percentages for categorical data. Categorical variables will be summarized as counts and percentages. All statistical parameters (eg, mean, median, standard deviation) will be tabulated together with their corresponding confidence intervals (CIs) and/or standard errors.

Continuous variables will be summarized as medians with first to third quartiles. Appropriate conventional statistical analyses will be used to assess the primary and secondary endpoints. Categorical data will be compared using χ^2 or Fisher’s exact test, as appropriate; some comparisons will require correction for potential confounders such as race/ethnicity; these will be performed using the Cochrane-Mantel-Haenszel test. Continuous variables will be compared using the Wilcoxon test or the t-test. The incidence of an adverse outcome (ie, graft rejection, graft loss, renal impairment, tacrolimus toxicities, and death) will be estimated using Kaplan-Meier curves. Depending on the distribution of the data, time-to-event (ie, time to reach therapeutic target range) analysis will be performed using an appropriate parametric, nonparametric, or semi-parametric survival analysis method. An ANOVA model may be utilized and tabulated along with the CIs. During the analysis, if a possible confounding variable was identified, the variable will be measured and entered into the analysis as a covariate.

Confounding factors that may impact tacrolimus response include race, age, and disease characteristics. It is possible that there may be differences in baseline demographics and disease states between the pharmacogenomic and control group. To minimize the potential impact of confounding variables on treatment response, an overall matching strategy has been incorporated into the design of the study. Please see [Section 8.4](#) for more information regarding the matching strategy.

The exploratory endpoints will be analyzed using descriptive statistics. No formal statistical testing is planned at this time.

Statistical testing, whenever performed, will be 2-sided with a significance (alpha) level of 0.05. In addition, 95% confidence intervals will also be determined. All statistical analyses will be conducted using SAS® or other appropriate statistical programs.

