8.4 Matching Strategy

As there are confounding variables, including age, race and disease state that may impact the results of the study, our study design incorporates an overall matching strategy, so that we can identify a well-matched control group. First, to control for differences in care over time, patients in the pharmacogenomic group will be matched to controls enrolled from 2010 to present. This time period was selected as there had been no major changes in standard of care or treatment regimen since 2010. After eligibility is met, control patients will be selected to match the pharmacogenomic group using a computerized matching algorithm that has been optimized to match baseline demographic and disease characteristics that have been identified a priori as likely to influence the treatment response to tacrolimus. To balance the trade-off between minimizing bias and maximizing matched sample size, a systematic approach will be conducted to identify the number of matched control patients for each patient in the pharmacogenomic group. This approach will include the following steps: 1) run the desired matching algorithm, starting with 1:1 (one control to one patient in the pharmacogenomic group) matching and iterating until the maximum desired number of potential controls per treated subject is reached; 2) for each iteration, test for covariate balance; and 3) generate numeric summaries and graphical plots of the balance statistics across all iterations in order to determine the optimal number (Linden and Samuels 2013).

The selection of patients for the control group using a matching algorithm will be conducted by an independent statistician in a blinded and unbiased manner. The statistician will have no knowledge of survival outcome, other outcome data, and genotype.

9 Safety and Adverse Events

Safety will be assessed throughout the study by evaluating physical exam, clinical chemistry, urinalysis, hematology, renal function, and incidence of adverse events (ie, graft rejection, graft loss, renal impairment, drug-related adverse events, tacrolimus toxicities, and death).

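### Controls are matched to each guided patient, but the primary endpoint is sized and tested as if the groups were independent, so the planned chi-square is conservative if matching works

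*Combined protocol and SAP*

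**What the plan says.** Section 8.4 states that "control patients will be selected to match the pharmacogenomic group using a computerized matching algorithm". The factors are ones judged in advance to influence response to tacrolimus. The number of controls per guided patient starts at 1:1, with the procedure "iterating until the maximum desired number of potential controls per treated subject is reached", and is then settled from balance statistics.

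Section 8.2 sizes the study on a two-sided chi-square test with "pharmacogenomics group = 130; control group = 130 patients" and "a 40% and 60% frequency of the primary endpoint in the control and pharmacogenomic group", and concludes that this "would be sufficient to provide a statistical power of 90% to detect a significant difference between the two groups".

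Section 8.3 assigns chi-square or Fisher's exact test to categorical data. For continuous data it says "Continuous variables will be compared using the Wilcoxon test or the t-test". It adds a Cochran-Mantel-Haenszel test for some comparisons (race/ethnicity is the example), leaves the survival method open, and lets confounders identified during the analysis enter as covariates. It mentions matching only as a design feature. Nowhere does the plan name McNemar's test, conditional logistic regression, stratification by matched set, or standard errors that allow for the sets.

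Sections 1 and 4.3 add that a few enrolled patients may be transplanted before their genotype result is available. They receive standard dosing and join the control group as prospective controls.

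**The concern.** Matching on factors that predict the outcome tends to make outcomes within a set alike. The variance of the difference between groups is then smaller than the independent-groups formula assumes. A chi-square or Fisher test that ignores the sets uses too large a standard error: p-values are too large, intervals are too wide, and precision bought by matching is given away. In a non-randomised comparison that relies on matching for its credibility, the analysis should say how the sets are used. If it does not, the choice between a matched and an unmatched analysis can be made after results are known, and section 6.2 says investigators are not blinded.

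**Working it through.** **Inputs.** From 8.2: 40% versus 60%, 130 per group, 90% power. From 8.3: "Statistical testing, whenever performed, will be 2-sided with a significance (alpha) level of 0.05". Assumed, because the documents give no value: 1:1 pairs and a within-pair outcome correlation r from 0 to 0.3.

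**Step 1: reproduce the plan's figure.** Independent groups, pooled variance, no continuity correction:

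n = [1.96·√(2·0.5·0.5) + 1.2816·√(0.24 + 0.24)]² / 0.20² = (1.3859 + 0.8879)² / 0.04 = 129.3, so 130 per group.

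Power at 130 is Φ[(0.20·√130 − 1.3859)/0.6928] = Φ(1.291) = 90.2%. The stated figure is reproduced exactly, by a formula that ignores the matching.

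**Step 2: true alpha of the unpaired test.** With n pairs and common proportion p, the difference has variance 2p(1−p)(1−r)/n, while the chi-square uses 2p(1−p)/n. Its z statistic therefore has variance 1−r under the null, and

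alpha = 2·[1 − Φ(1.96/√(1−r))].

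- r = 0: 2·[1 − Φ(1.96)] = 5.0%
- r = 0.1: 2·[1 − Φ(2.066)] = 3.9%
- r = 0.3: 2·[1 − Φ(2.343)] = 1.9%

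Simulation (200,000 replicates of 130 pairs, 40% in both groups) gives 5.1%, 3.9% and 1.9%.

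**Step 3: interval width.** The unpaired interval is too wide by a factor 1/√(1−r): 1.00, 1.05 and 1.20. Under 40% versus 60%, the simulated mean width of the unpaired 95% interval is 0.237 throughout. The paired interval is 0.237, 0.225 and 0.198 wide. Coverage of the unpaired interval is 94.3%, 95.5% and 97.6%.

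**Step 4: power of both tests on the same 130 pairs.** The probability that both members succeed is 0.24 + 0.24r, so the discordant proportion is d = 0.52 − 0.48r. For McNemar,

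pairs = [1.96·√d + 1.2816·√(d − 0.04)]² / 0.04.

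| r | d | Pairs for 90% power | Simulated power, chi-square | Simulated power, McNemar |
|---|---|---|---|---|
| 0 | 0.520 | 133 | 90.7% | 89.9% |
| 0.1 | 0.472 | 120 | 91.9% | 92.6% |
| 0.3 | 0.376 | 95 | 94.4% | 97.3% |

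The like-for-like gain is under 1 point at r = 0.1 and about 3 points at r = 0.3. At r = 0 there is a loss of about 1 point, or 3 more pairs than planned.

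**Step 5: how plausible is r?** With two equal strata averaging 40%, stratum rates are 0.40 ± √(0.24r). So r = 0.1 needs about 25% and 55%, and r = 0.3 needs about 13% and 67%. As an illustration, take the variant allele frequencies in 4.4 (33% in African Americans, 82% to 95% in Whites). Nonexpresser frequencies are then 0.33² = 11% and 0.82² to 0.95² = 67% to 90%. With 40% to 50% African Americans and an assumed 30-point gap in target attainment between nonexpressers and expressers, matching on race alone gives r of about 0.03 to 0.06. Matching on age and disease could add to this.

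**The case against.** The strongest reply is that this is under-specification with a mild, safe consequence. Much of that stands.

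- A reader might infer that every planned test is unpaired. The documents do not say so: the form of the Wilcoxon and t-tests is not stated, and the survival method is open. Only the chi-square and Fisher tests, which apply to the primary endpoint, are definitely for independent groups.
- The Cochran-Mantel-Haenszel test and covariate adjustment could recover part of the lost precision. That is true, but 8.3 provides the former for some comparisons only and picks covariates during the analysis. Neither is tied to the matched sets.
- A reader might set McNemar's calculated 92% to 97% power against the stated 90%. That is not like for like, because the chi-square also gains power on correlated pairs (Step 4).
- A reader might infer that unequal set sizes bias the comparison. Section 8.4 reads most naturally as choosing one common ratio, and 8.2 plans 130 against 130. The bias arises only if set sizes vary, and the documents give no basis for sizing it.
- A reader might infer that prospective controls have no matched partner. Section 8.1 describes the whole control group as matched, while 4.3 has these patients enter because of genotype timing. Their matching is unclear, not ruled out.
- A strictly paired analysis would drop unmatched patients, and pairs with one missing level, against the ITT statement in 8.3. This stands, and the fix has to respect it.

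**Conclusion.** The point holds for the primary endpoint. Matching is done per guided patient, the primary test and the sample size assume independence, and nothing carries the matched sets into the analysis. The standard error is therefore wrong for the design whenever matching induces correlation.

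The size is modest and uncertain. For assumed correlations of 0 to 0.3, true alpha is 5.0% down to 1.9%, and intervals are 0% to 20% too wide. At the low end the effect is negligible. These figures rest on 1:1 pairs and non-negative correlation; 1:k matching was not simulated.

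It would be wrong to conclude that the trial risks false positives from this source, or that its sample size fails. The error is conservative, and 260 patients remain adequate apart from about 3 more pairs for McNemar at zero correlation. For the secondary comparisons the gap is that the paired or unpaired form is not stated.

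**What to change.** In 8.3, base the primary comparison on the matched sets: a risk difference with a 95% confidence interval and test from standard errors clustered by matched set. McNemar's test (1:1) or conditional logistic regression (1:k) are alternatives. If set sizes vary, weight controls by set. Apply the same set-robust approach to the secondary comparisons, and state the form of the Wilcoxon and t-tests.

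Keep every ITT patient in the primary estimate. Treat any unmatched prospective control or guided patient as its own cluster, with adjustment for the matching variables. Those variables need one fixed list, since race is included in 1, 4.3 and 8.4 but omitted in 5.3, 8.1 and 10.4.2. Report the ordinary chi-square as a sensitivity analysis.

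The cost is SAP wording, slightly more analysis work, and a negligible loss of power if the within-set correlation is about zero.

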3.2 Secondary Endpoints

The secondary endpoints are described below.

- The incidence of BPAR within the first 3 months, 3-6 months, 6-9 months, and 6-12 months after transplantation
- Time to achieve tacrolimus therapeutic range at 0 to 4 months (8-10 ng/mL)
- Proportion of patients who had dose adjustments and/or drug alteration or addition due to insufficient immunosuppression
- Incidence of acute and chronic renal impairment. Renal function will be assessed using estimated Glomerular Filtration Rate (eGFR). Creatinine clearance (CrCl) may also be calculated as a reference. Patients will be categorized as having either mild (eGFR of 60 mL/min/1.73m² to 89 mL/min/1.73m²), moderate (eGFR of 30 mL/min/1.73m² to 59 mL/min/1.73m²), or severe renal impairment (eGFR <30 mL/min/1.73m²).
- Incidence of adverse outcomes (ie, graft rejection, graft loss, renal impairment, adverse drug events, tacrolimus toxicities, and death)

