As the arrival of the donor kidney may come quickly and unexpectedly, it is possible that enrolled subjects may receive kidney transplantation prior to the incorporation of the *CYP3A5* genotype result into EMR. In this case, patients will receive tacrolimus based on current standard tacrolimus dosing (0.1 mg/kg/day given in two divided doses) and will be included in the control group (prospective controls). Throughout the study, safety and efficacy measures will be evaluated in the prospective controls per UNC-CH kidney transplant procedure. These patients will also be followed from Study Day 2 and up to 12 months from the initiation of the first tacrolimus dose to assess long-term outcome (Follow-up Period).

Additionally, age-, race-, and disease-matched patients who had previously received kidney transplantation with standard tacrolimus dosing will also be asked to give consent for genotyping (historical controls). These patients will also be included in the control group and their safety and efficacy data will be collected retrospectively for up to 12 months from the initiation of first tacrolimus dose. Hence, the control group will consist of both historical controls and potentially few prospective controls, if the scenario described above occurred.

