5.3 Patient Recruitment and Screening

Patients receiving pretransplant care for kidney transplantation at UNC-CH will be screened for eligibility based on the inclusion/exclusion criteria described in [Sections 5.1](#) and [5.2](#). Following acquisition of consent, buccal swab samples will be collected for genotyping. Eligible patients who consented will receive genotype-guided dose for the initial tacrolimus dosing following kidney transplantation.

Subsequent tacrolimus dosing will then be adjusted according to trough concentrations and therapeutic target concentrations.

For the historical controls, age- and disease-matched patients who had previously received kidney transplantation with standard tacrolimus dosing will also be asked to give consent for genotyping (historical controls) during one of their post-transplant visit. Eligible patients who consented will be included in the control group and their safety and efficacy data will be collected retrospectively for up to 12 months from the initiation of first tacrolimus dose.

In addition, to be able to effectively compare outcomes between expressers and nonexpressers as well as between pharmacogenomic and control groups, we will make every effort to enroll African Americans to the study, including showing genuine interest to subjects' well-being during one-on-one interactions, referring to them by their last names until given permission to use their first names, and using noninvasive means to collect samples (Johnson et al. 2011; Spence and Oltmanns 2011), so as to get equal numbers of Caucasians and African Americans in our study.

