10.4.2 Historical Data

Historical data from the control group will be obtained from 2010 until the end of study period. The historical controls will consist of age- and disease-matched patients who met eligibility criteria and have had previously

received kidney transplantation with standard tacrolimus dosing. These patients will also be asked to give consent for genotyping during a standard routine follow-up visit post-transplantation. Eligible patients who consented will be included in the control group and their safety and efficacy data will be collected retrospectively for up to 12 months from the initiation of the first tacrolimus dose.

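### Kaplan-Meier curves drawn separately for rejection, graft loss, renal impairment and tacrolimus toxicities would slightly overstate their 12-month incidence, because death is a competing event

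*Combined protocol and SAP*

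**What the plan says.** Section 8.3 assigns one estimator to a list of five outcomes: "The incidence of an adverse outcome (ie, graft rejection, graft loss, renal impairment, tacrolimus toxicities, and death) will be estimated using Kaplan-Meier curves". The matching secondary endpoint in Section 3.2 is "Incidence of adverse outcomes (ie, graft rejection, graft loss, renal impairment, adverse drug events, tacrolimus toxicities, and death"). So incidence is the target, and Kaplan-Meier is the estimator named for it. Neither section says whether the list is one composite or a set of separate outcomes. Neither says how a death or a graft loss is handled in the curve for another outcome. Cumulative incidence functions and competing risks appear nowhere in the document.

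Two other passages bear on the point. Biopsy-proven acute rejection is also a separate endpoint, counted in fixed windows: "The incidence of BPAR within the first 3 months, 3-6 months, 6-9 months, and 6-12 months after transplantation". Follow-up and consent differ by group. The pharmacogenomic group consents before transplant and is followed forward. Historical controls, according to Section 5.3, "will also be asked to give consent for genotyping (historical controls) during one of their post-transplant visit", and "their safety and efficacy data will be collected retrospectively for up to 12 months from the initiation of first tacrolimus dose". Section 10.4.2 repeats the consent arrangement without setting a minimum time since transplant. Section 4.3 adds that "the control group will consist of both historical controls and potentially few prospective controls".

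**The concern.** A patient who has died can no longer have a rejection, a graft loss, renal impairment or a toxicity. A patient who has lost the graft can no longer reject it. A Kaplan-Meier curve for one of these outcomes treats such patients as censored, that is, as if they could still have the event later at the same rate as those still under observation. One minus Kaplan-Meier then estimates the incidence in a hypothetical setting without deaths, which is higher than the share of patients who actually have the event.

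What is at stake is the accuracy of the 12-month secondary and safety summaries. The primary endpoint, a proportion on Day 3 and Day 7, is not touched.

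**Working it through.** **The plan's own figure.** Section 8.2 gives 130 per group for 40% versus 60%, 90% power and a two-sided 5% χ² test. With pooled variance:

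n = [1.960·√(2·0.5·0.5) + 1.2816·√(0.4·0.6 + 0.6·0.4)]² / 0.20² = 129.3, rounded up to 130; power at 130 is 90.2%.

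The figure reproduces and does not depend on the Kaplan-Meier sentence. It is used here only for the group size.

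**Inputs for the bias.** The follow-up of 12 months and the 130 per group come from the documents. The event rate F1 and the competing-event rate F2 (death, or death plus graft loss for rejection) are assumptions, because the documents give neither. The range taken is F1 10-30% and F2 1-10%.

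**Formula.** With constant cause-specific hazards over 12 months, the total cumulative hazard is L = −ln(1 − F1 − F2), and the share belonging to the event is F1/(F1 + F2). Hence

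1 − KM = 1 − (1 − F1 − F2)^(F1/(F1+F2)).

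Example, F1 30% and F2 5%: 1 − 0.65^(0.30/0.35) = 1 − 0.6913 = 30.87%, an excess of 0.87 points. Example, F1 30% and F2 10%: 1 − 0.60^0.75 = 1 − 0.6817 = 31.83%, an excess of 1.83 points.

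Excess of one minus Kaplan-Meier over the true 12-month incidence, in percentage points:

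| F1 | F2 1% | F2 3% | F2 5% | F2 10% |
|---|---|---|---|---|
| 10% | 0.05 | 0.16 | 0.27 | 0.56 |
| 20% | 0.11 | 0.33 | 0.56 | 1.16 |
| 30% | 0.17 | 0.52 | 0.87 | 1.83 |

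**Sensitivity to timing.** If all competing events came before any event of interest, one minus Kaplan-Meier would be F1/(1 − F2). At F1 20% and F2 5% this is 21.05%, an excess of 1.05 points; at F1 30% and F2 10% it is 33.33%, an excess of 3.33 points. The constant-hazard figures can therefore roughly double, but not more.

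**Against sampling error.** The 95% CI half-width for a difference at 130 per group is 1.96·√(2·F1·(1 − F1)/130): 7.3 points at F1 10%, 9.7 at 20% and 11.1 at 30%.

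**Between groups.** Take the extreme case in which 5% die in the guided group and no control deaths are observed.

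- Equal true incidence of 30% in both groups: Kaplan-Meier gives 30.87% against 30.00%, a false 0.87 points against guided dosing.
- Equal event hazard in both groups, so that Kaplan-Meier gives 30% in each: the event's cumulative hazard is −ln(0.70) = 0.3567, and a death incidence of 5% needs a cumulative death hazard of 0.0612. The cumulative incidence in the guided group is (0.3567/0.4178)·(1 − e^(−0.4178)) = 0.8536·0.3415 = 29.15%, against 30.00% in controls. Kaplan-Meier is balanced here, and the cumulative incidence function differs by 0.85 points in favour of guided dosing.

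The sign depends on which quantity is equal in the two groups, and nothing in the documents settles that.

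**The case against.** The strongest defence is that the document never says that deaths or graft losses are censored. The sentence in Section 8.3 can be read as time to the first adverse outcome of any kind, death included. On that reading Kaplan-Meier is valid and the overstatement is zero. This cannot be excluded, but separate curves are the more natural reading. Section 3.2 lists outcomes in the plural, Section 8.3 speaks of curves, the list is nowhere called a composite, and rejection and renal impairment are also endpoints in their own right. Under either reading the text needs a sentence.

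A second defence is that Section 8.3 also provides counts, percentages and χ² or Fisher tests for categorical data, and the windowed rejection endpoint fits those. With complete 12-month follow-up a crude proportion equals the Aalen-Johansen estimate, and Section 8.2 expects dropout below 5%. This stands: a correct crude figure could appear next to the Kaplan-Meier one. It does not remove the mismatch in the sentence that names the estimator.

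Three stronger readings are tempting, and the documents do not support them:

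- **Only the guided group can have deaths.** Prospective controls are followed forward. A historical control who consents before month 12 can also die within the window, since no minimum time since transplant is set. Deaths will be seen mainly in the guided group, not only there.
- **The method is biased against guided dosing.** As shown above, this requires equal cumulative incidences; under equal hazards it does not hold.
- **Censored graft losses inflate the graft-loss curve.** Only death competes with graft loss.

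Lastly, Section 5.3 says historical controls "will also be asked to give consent for genotyping (historical controls) during one of their post-transplant visit", which selects them for survival to that visit. The blinding of the matching statistician in Section 8.4 does not undo this, because it acts on patients who are already eligible. It is a separate problem, and a change of estimator does not repair it.

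**Conclusion.** The point holds as a minor one, on the condition that each outcome has its own curve. In that case one minus Kaplan-Meier overstates the 12-month incidence of rejection, graft loss, renal impairment and tacrolimus toxicities. The excess is about 0.05 to 0.9 points for event rates of 10-30% with 1-5% competing events, and up to about 1.8 points with 10% competing events. These sizes rest on assumed rates and constant hazards.

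The bias is well inside the sampling error of the comparison and is unlikely to change a conclusion. For death alone, and for a composite that includes both death and graft loss, there is no overstatement of this kind. No direction of between-group bias should be claimed. Sample size, power and the primary endpoint are unaffected. It is a free improvement.

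**What to change.** In Section 8.3:

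1. State which adverse outcomes are analysed separately and which, if any, form a composite, and give the censoring rule for each.
2. Estimate each non-fatal outcome (rejection, graft loss, renal impairment, tacrolimus toxicities) with the Aalen-Johansen cumulative incidence function. Treat death as a competing event for all of them, and graft loss also as a competing event for rejection.
3. Report the 12-month difference between groups with a 95% CI.
4. Keep Kaplan-Meier for death and for composites that include death, such as death or graft loss.
5. Note in the report that historical controls had to be alive at a post-transplant visit to consent, and that the estimator does not correct for this.

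The cost is a few sentences in the SAP and a standard software option. The only inputs are dates of death, graft loss and each event, all of which are outcomes the plan already covers, so no new data are needed.
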